15. PHOTOGRAPHY

Standardized photography of facial rosacea at Baseline, and at the site visits at Weeks 2, 4, 8 and 12 (End of Study) will be performed at select sites. These photographs will be optional for patients at the selected sites and will not be used for efficacy assessment purposes. Participating investigators shall refer to separate photographic manual for instructions.

16. SAFETY EVALUATIONS

Safety will be assessed by monitoring incidence of Cutaneous Safety Assessment, Local Tolerability Assessment and adverse events reporting; at Baseline, at all treatment and end-of-treatment visits.

16.1. Cutaneous Safety Assessments

The evaluator will assess local application site cutaneous reactions by rating the dryness and scaling at the Baseline visit and site visits at Weeks 2, 4, 8 and 12 (End of Study) or unscheduled visits. The evaluator will determine the score for each of these variables by direct evaluation. The definitions of grades provided in Table 4 will be applied to these evaluations. The Cutaneous Safety Assessment of dryness and scaling will be made by the investigator at the time of the visit.

Table 4: Cutaneous Safety Assessment Scale

Grade	Description
Dryness	
0 – None	No dryness
1 – Mild	Slight but definite dryness
2 – Moderate	Moderate dryness
3 – Severe	Marked dryness and/or cracking
Scaling	
0 – None	No scaling
1 – Mild	Barely perceptible scaling
2 – Moderate	Obvious but not profuse scaling
3 – Severe	Heavy scale production and/or peeling

Application site reactions (dryness and scaling) are not to be recorded as adverse events unless they result in either:

- The temporary discontinuation of the study product.
- The discontinuation of the patient from the study.
- The use of a new concomitant medication in order to treat this event.

Any other application site reaction not listed above (such as pain) should be recorded as adverse events in the source document and eCRFs.

16.2. Local Tolerability Assessments

The evaluator will assess local application site tolerability by rating the itching and burning/stinging at the Baseline visit and site visits at Weeks 2, 4, 8 and 12 (End of Study) or unscheduled visits. The evaluator will determine the score for each of these variables by asking the patient to grade their experience over the **past 24 hours**. The definitions of grades provided in [Table 5](#) will be applied to these evaluations. The Local Tolerability Assessment evaluations of itching and burning/stinging will be made by the investigator at the time of the visit.

Table 5: Local Tolerability Assessment Scale

Grade	Description
Itching	
0 – None	No itching
1 – Mild	Slight itching, not really bothersome
2 – Moderate	Definite itching that is somewhat bothersome
3 – Severe	Intense itching that may interrupt daily activities and/or sleep
Burning/Stinging	
0 – None	No burning/stinging
1 – Mild	Slight burning/stinging sensation; not really bothersome
2 – Moderate	Definite warm, burning/stinging sensation that is somewhat bothersome
3 – Severe	Hot burning sensation that causes definite discomfort and may interrupt daily activities or sleep

Application site reactions (itching and burning/stinging) are not to be recorded as adverse events unless they result in either:

- The temporary discontinuation of the study product.
- The discontinuation of the patient from the study.
- The use of a new concomitant medication in order to treat this event.

Any other application site reaction not listed above should be recorded as adverse events in the source document and eCRFs.

17. ADVERSE EVENTS

17.1. Departure from the Protocol for Individual Patients

When an emergency occurs requiring a departure from the protocol for a patient, departure will be only for that patient. In such circumstances, the investigator or other physician in attendance will contact the Medical Monitor or the Sponsor by telephone and follow up with a written description as soon as possible. The overseeing IRB should also be notified.

17.2. Definitions

An adverse event (AE) is defined as any untoward medical occurrence in a patient administered a medicinal product and which does not necessarily have to have a causal relationship with this treatment. An adverse event can therefore be any unfavorable and unintended sign, symptom, or disease temporally associated with the use of a medicinal product, whether or not considered related to this medicinal product.

A serious adverse event (SAE) is an adverse event that results in any of the following outcomes:

- Death
- Life-threatening event (i.e., the patient was, in the opinion of the investigator, at immediate risk of death from the event as it occurred. It does not include an event that, had it occurred in a more severe form, might have caused death)
- Requires in-patient hospitalization or prolongs hospitalization
- A persistent or significant disability/incapacity or substantial disruption of the ability to conduct normal life functions
- Congenital anomaly/birth defect
- Other adverse events that may be considered serious based upon appropriate medical judgment, may jeopardize the patient and may require medical or surgical intervention to prevent one of the outcomes listed above.

Immediately Reportable Adverse Events (IRAE) is any serious AE or any AE that necessitates discontinuation of study product, including pregnancy.

Unexpected Adverse Event is any adverse drug experience, the specificity or severity of which is not consistent with the current approved product labeling (package insert) for the study product, the Investigator's Brochure, or as described in the clinical protocol and consent materials.

Intensity of Adverse Events are the maximum intensity of an AE during a day should be recorded on the eCRF. If the intensity of an AE changes over a number of days, then separate entries should be made having distinct onset dates for the changes in severity.

- Mild - AEs are usually transient, requiring no special treatment, and do not interfere with patient's daily activities.
- Moderate - AEs typically introduce a low level of inconvenience or concern to the patient and may interfere with daily activities, but are usually ameliorated by simple therapeutic measures.
- Severe - AEs interrupt a patient's usual daily activity and traditionally require systemic drug therapy or other treatment.

17.3. Causal Relationship to Study product

The following criteria should be used in assessing the apparent causal relationship of an AE to study product:

Definitely - The AE:

- follows a reasonable temporal sequence from study product administration
- abates upon discontinuation of the study product (de-challenge)
- is confirmed by reappearance of the reaction on repeat exposure

Probably - The AE:

- follows a reasonable temporal sequence from study product administration
- abates upon discontinuation of the study product (de-challenge).
- cannot be reasonably explained by the known characteristics of the patient's state.

Possible - The AE:

- follows a reasonable temporal sequence from study product administration
- but that could readily be produced by a number of other factors.

Unlikely - The AE:

- follows a reasonable temporal sequence from study product administration.
- could have been produced by either the patient's clinical state or by study product administration.

Not related - The AE:

- does not have a reasonable temporal association with the administration of study product
- has some other obvious explanation for the event.

17.4. Eliciting and Reporting of Adverse Events

The investigator will periodically assess patients for the occurrence of adverse events. In order to avoid bias in eliciting adverse events, the patient or parent/legally authorized representative should be asked a non-specific question (e.g., "How have you been feeling since your last visit?") to assess whether any AE has been experienced since the last visit. All adverse events (as defined in [Section 17.2](#)), either observed by the Investigator or one of his/her medical collaborators, or reported by the patient spontaneously, or in response to direct questioning, will be reported and documented in the source and the study reporting forms. When reporting an adverse event, the Investigator must assign a severity grade to each event and declare an opinion on the relatedness of the event to the study product or procedure. Serious or unexpected adverse events must be reported to the CRO within 24 hours of when the Investigator first learns of the occurrence of the event.

Adverse events will be documented in the source document and recorded in a timely manner on case report forms. Adverse events that are identified at the last assessment visit (or the Early Termination Visit) must be recorded on the AE eCRF with the status of the AE noted.

Adverse event reporting begins from the signing of informed consent/assent. Study product-related adverse events should be followed until resolved or 30 days after the final study treatment. Regardless the duration of the study, patients that exhibit serious adverse event (SAE), will be followed up until the SAE resolves, based on investigator's medical judgment or are considered to be chronic (stabilized for at least 30 days). All events that are ongoing at this time will be recorded as ongoing on the eCRF.

17.5. Expedited Reporting Responsibilities of the Study Center

For any serious or unexpected adverse event, the Sponsor or its designee must be notified within 24 hours of when the Investigator first learns of the occurrence of the event. Expedited reporting requirements for serious adverse events are described below. Adequate information must be collected with supporting documentation to complete a standard report for submission to Sol-Gel. The adverse event term on the AE eCRF and the SAE report should agree exactly. Special attention should be given to recording hospitalizations and concomitant medications.

Patients with unresolved study or product-related adverse event(s) or serious adverse event(s) should be followed by the investigator until the events are resolved, events determined to be chronic or the patient is lost to follow-up. Resolution means the patient has returned to the Baseline state of health, or the investigator does not expect any further improvement or worsening of the adverse event. The investigator should continue to report any significant follow-up information to the sponsor up to the point that the event has resolved. Any serious adverse event reported by the patient to the investigator that occurs within 30 days after the last assessment, and are determined by the investigator to be reasonably associated with the use of the study product, should be reported to the sponsor within 24 hours of when the Investigator first learns of the occurrence of the event.

When reporting a serious adverse event (SAE) the Investigator (or the Study Coordinator) will promptly report any serious adverse event or pregnancy to the Sponsor or its designee by telephone email, immediately after the investigator becomes aware of the event. An SAE form should be completed and sent by fax, email, or overnight courier to the Sponsor or its designee within 24 hours of knowledge of the event by the site. In many cases, only preliminary information will be available. Appropriate follow up information should be sought (hospital discharge summaries, operative reports etc.) and a follow up SAE report form submitted. A designation of causality from the study product should always be included with a follow up report. Assess and report the causality of the event.

17.6. Submitting an Expedited Safety Report to the IRB

Once all supporting documentation is received for the reported event, the Medical Monitor, in conjunction with Sol-Gel, will determine if the safety report is eligible for expedited review. When expedited safety reporting to regulatory authorities is indeed required, the Investigator should review and update any newly available materials at once. Follow-up queries may be sent to the study center to further clarify the event.

The Sponsor, or its designee, is responsible for submitting reports of serious, unexpected related AEs to regulatory authorities on an expedited basis, according to the ICH E2A Guideline and to other regulatory authorities according to national and local regulations as required. The Sponsor, or its designee, is responsible for prompt submission to the IRB or EC of any expedited SAE reports submitted to regulatory authorities. All investigators participating in ongoing clinical studies will receive copies of the SAE reports submitted on an expedited basis to regulatory authorities

17.7. SAE & AEs Requiring Discontinuation of Study Drug, including Pregnancies

ANY SAE, WHICH OCCURS AFTER A PATIENT HAS ENTERED THE STUDY, WHETHER OR NOT RELATED TO STUDY PRODUCT, MUST BE REPORTED TO THE SPONSOR OR ITS DESIGNEE IMMEDIATELY (WITHIN 24 HOURS) VIA TELEPHONE, EMAIL OR FACSIMILE. IF INITIALLY REPORTED VIA TELEPHONE, THIS MUST BE FOLLOWED-UP BY A FACSIMILE OR EMAIL OF THE WRITTEN SAE REPORT WITHIN 24 HOURS OF THE CALL TO THE SPONSOR OR ITS DESIGNEE.

Non-serious events that require discontinuation of study product (including laboratory abnormalities) should be reported to the Sponsor or its designee immediately and within 1 working day.

Patients who discontinue due to experiencing study product-related adverse events should be followed clinically until their health has returned to baseline status, or until all parameters have returned to normal. It is expected that the investigator will provide or arrange appropriate supportive care for the patient.

A patient who experiences a severe adverse event related to study product will be discontinued from the study, but, regardless of the duration of the study, patients that exhibit serious adverse event (SAE), will be followed up until the SAE resolves, based on investigator's medical judgment or are considered to be chronic (stabilized for at least 30 days). For safety reporting instructions see SAE and Pregnancy Form Report Instructions.

17.8. Pregnancy

At the time, Principal Investigator or site personnel becomes aware that a study patient became pregnant following study participation, the Principal Investigator or designee will report the pregnancy immediately by phone and/or by faxing a completed Pregnancy Report to the Sponsor or its designee within one working day of being notified of the pregnancy report.

The report will include the following elements:

- Patient (mother's) coded study identifier;
- Date of patient's last menstrual period;
- Total accumulated dose of study treatment administered to date;
- Date of study product administration.

The investigator will follow the patient until completion of the pregnancy and must assess the outcome in the shortest possible time but not more than 30 days within completion of the pregnancy.

Upon delivery, miscarriage or abortion, the Principal Investigator or designee must forward a follow-up Pregnancy Report with any relevant information on the present condition of the fetus to the Sponsor or its designee, including:

- Mother's coded study identifier(s);
- Gestational age at delivery, miscarriage or abortion;
- Birth weight, gender, length and head circumference, if available;
- Apgar scores recorded after birth, if available;
- Any abnormalities.

If the outcome of the pregnancy meets the criteria for immediate classification of an SAE (e.g., spontaneous or therapeutic abortion [any congenital anomaly detected in an aborted fetus is to be documented], stillbirth, neonatal death, or congenital anomaly), the investigator will report the event by phone and by faxing a completed SAE report form to the Sponsor or its designee within one working day of being notified of the pregnancy report.

If the trial is completed before the outcome of the pregnancy is known, the Sponsor or its designee will assume the responsibility for following up on the pregnancy. The Sponsor or its designee will contact the Investigator or Study coordinator on or around the potential expected date of delivery to follow-up on the outcome of pregnancy and will also check on the status of the infant 8 weeks post-delivery. Upon awareness of the pregnancy outcome and known status of the infant following 8 weeks of delivery, the investigator will complete the applicable pregnancy report forms and fax to the Sponsor or its designee within 1 day of being notified.

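### Protocol section 17.8 gives one working day, counted from the wrong event, to send the SAE form for a serious pregnancy outcome; section 17.5 gives 24 hours for that form

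*Protocol*

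**What the plan says.** Section 17.8 of the Protocol covers pregnancy. Its SAE paragraph opens "If the outcome of the pregnancy meets the criteria for immediate classification of an SAE" and gives examples: spontaneous or therapeutic abortion, then "stillbirth, neonatal death, or congenital anomaly". In those cases the investigator reports by telephone and also in writing, "by faxing a completed SAE report form to the Sponsor or its designee within one working day of being notified of the pregnancy report".

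Three other sections hold the general SAE rules.

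- Section 17.4: serious or unexpected events "must be reported to the CRO within 24 hours of when the Investigator first learns of the occurrence of the event". This limits the report and does not mention a form.
- Section 17.5: "An SAE form should be completed and sent by fax, email, or overnight courier to the Sponsor or its designee within 24 hours", counted from the site's knowledge of the event. The sentence before it covers serious events and pregnancies together and asks for prompt reporting as soon as the investigator is aware.
- Section 17.7, headed "SAE & AEs Requiring Discontinuation of Study Drug, including Pregnancies": any SAE after study entry, related or not, must be reported within 24 hours. If the first report is by telephone, the written SAE report follows within 24 hours of the call. One working day appears here only for non-serious events that require stopping study product.

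**The concern.** One event, such as a miscarriage during the study, is governed by two deadlines for the same form to the same recipient. The looser one stands in the section that a site would open first when dealing with a pregnancy. A working-day limit stretches over weekends and holidays; a 24-hour limit does not. Section 17.8 thus gives a serious outcome the kind of limit that 17.7 keeps for non-serious events.

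The start of the 17.8 clock is also wrong. It names notice of the pregnancy report, the same trigger that 17.8 uses for the initial notification of a pregnancy. The outcome comes later, possibly by months, so on a literal reading the SAE deadline could expire before there is an SAE to report.

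What is at stake is timeliness. Under section 17.6 the sponsor or its designee sends expedited reports to regulators, and that work cannot start until the site has reported.

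**Working it through.** No statistical figure is involved. The check is a comparison of the text, followed by calendar arithmetic.

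**Step 1: do the rules cover the same event?** Section 17.8 itself classes the listed outcomes as SAEs. One of them also stands in the general definition in 17.2 ("Congenital anomaly/birth defect"). Sections 17.4, 17.5 and 17.7 contain no pregnancy exception, and 17.8 claims no precedence. For an outcome during the study, both sets of rules apply.

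**Step 2: which section sets a limit for the form?**

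| Section | What is limited | Limit |
|---|---|---|
| 17.4 | Report to the CRO | 24 h |
| 17.5 | SAE form | 24 h from site knowledge |
| 17.7 | First report of any SAE | 24 h |
| 17.7 | Written report after a phone report | 24 h from the call, so up to 24 + 24 = 48 h in all |
| 17.8 | Phone report and SAE form | One working day from notice of the pregnancy report |

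The direct conflict over the form is therefore between 17.5 and 17.8.

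**Step 3: how far apart are the limits?** The Protocol does not define a working day. I assume a Monday-to-Friday week and, to make the comparison possible, start the 17.8 clock when the site learns of the outcome. Two readings of one working day are shown:

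- Reading A, same clock time on the next working day: hours = 24 × calendar days to the next working day.
- Reading B, notice at 09:00 and deadline at 17:00 on the next working day: hours = reading A + 8.

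| Site learns of the outcome on | Days to next working day | Reading A | Reading B | 17.5 form limit |
|---|---|---|---|---|
| Sunday to Thursday | 1 | 24 h | 32 h | 24 h |
| Saturday | 2 | 48 h | 56 h | 24 h |
| Friday | 3 | 72 h | 80 h | 24 h |
| Friday before a Monday holiday | 4 | 96 h | 104 h | 24 h |

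Under reading A the excess over 17.5 is 48 − 24 = 24 h for Saturday, 72 − 24 = 48 h for Friday and 96 − 24 = 72 h before a Monday holiday. From Sunday to Thursday there is none (8 h under reading B). Against the 48 h that 17.7 can allow for the written report, Saturday shows no excess under reading A, but Friday still exceeds it by 72 − 48 = 24 h.

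**The case against.** The strongest defence is that the rules are compatible: a site that reports within 24 hours satisfies every section. Section 17.5 also asks for immediate reporting, and 17.7 states its rule in capitals. Delay needs a site that reads 17.8 alone. Section 17.7 also refers sites to separate SAE and pregnancy form instructions, which are not among the documents and may settle the matter. All of this limits the practical harm. It does not make the looser limit or its trigger correct.

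Section 17.8 could also be read as a special rule for pregnancy. The text gives it no such status.

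Three stronger readings are tempting but not supported.

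- A reader might infer that every other section sets 24 hours for the form. Only 17.5 does. Section 17.4 limits the report, and 17.7 gives the written report a further 24 hours after a phone call.
- Because congenital anomaly appears in both 17.2 and 17.8, a reader might infer that outcomes at birth fall squarely under both clocks. Patients must test negative at Screening and Baseline and treatment lasts 12 weeks, so such outcomes would normally come months after the last assessment. There, 17.5 attaches its 24 hours to product-associated SAEs within 30 days, and 17.9.2 states no deadline. The wording of 17.7 is broader, but the sections are not reconciled on this.
- Section 17.8 also asks for routine pregnancy forms by "fax to the Sponsor or its designee within 1 day of being notified", so a reader might infer that over a weekend the routine form falls due before the SAE form. That limit also waits for the infant's status 8 weeks after delivery, so an SAE known at delivery has its form due well before then.

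A reader might also pair this with the different end points for following related adverse events in 17.4 and 17.5. Section 17.4 has events still open recorded as ongoing, which supports reading its 30 days as a data cut-off. That is too weak to carry a change.

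**Conclusion.** The inconsistency is real but minor. Section 17.8 sets a looser limit for the SAE form than 17.5 does, and starts it from the wrong event. The clear case is narrow: a miscarriage or abortion during the study, learned of on a Friday or Saturday. The limit is then about 48 to 72 hours, or 96 before a Monday holiday, against 24 in 17.5. These figures rest on an assumed Monday-to-Friday week and the same-time reading of a working day; the end-of-day reading adds 8 hours throughout.

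The documents give no basis for a patient count, but few are likely to be affected. Nothing in the efficacy analysis or sample size depends on this. The one-working-day limit for the initial pregnancy notification is not in question; it matches the 17.7 limit for non-serious events that require stopping study product.

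**What to change.** In section 17.8, replace the end of the SAE sentence, from the time limit onward, with: *within 24 hours of first learning of the pregnancy outcome*. This corrects both the length of the limit and its starting point.

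Leave the initial pregnancy notification, the telephone allowance in 17.7 and the follow-up rules in 17.4 and 17.5 as they are. A form sent within 24 hours of learning of the outcome meets the time limit in each of these sections.

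The cost is one phrase of amendment or clarification text and a memo to sites, with no new procedure. The one added burden is that a site may have to send a form over a weekend, including for an outcome learned of after the study, where 17.9.2 currently sets no deadline. The separate SAE and pregnancy form instructions should be checked for the same wording.
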